### Definition of on-treatment period:

On-treatment period is defined as the time from the first study intervention to the last study intervention date + 30 days OR the earliest date of subsequent anticancer therapy minus 1 day, whichever occurs first, unless otherwise stated. For participants with treatment ongoing at cut-off date, all data from the first study intervention up to the cut-off date will be considered under the on-treatment period.

For immune-related AEs as listed in Section 15.2.4.2, an expanded on-treatment period will be used as a default for any analysis:

Time from the first study intervention to the last study intervention date + 90 days, death OR to the earliest date of subsequent anticancer therapy minus 1 day, whichever occurs first, unless otherwise stated.

Any systemic anticancer therapy, any anticancer surgery and any anticancer radiotherapy as documented in the "Anti-cancer treatment after discontinuation" CRF page will be considered as subsequent anticancer therapy.

The on-treatment period will include the initial treatment period as well as the reinitiation of treatment period, as applicable. Whether a participant reinitiates treatment (following the rules as outlined in the protocol) or not, the on-treatment period is defined as the time from the first study intervention administration to the last study intervention administration date + 30 days or the earliest date of subsequent anticancer drug (anticancer therapy, anticancer surgery and anticancer radiotherapy) therapy minus 1 day, whichever occurs first, unless otherwise stated.

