#### 9.4.2 Safety Analyses

The on-treatment period is defined as the time from the first study intervention administration to the last study intervention administration date + 30 days or the earliest date of subsequent anticancer drug therapy minus 1 day, whichever occurs first, unless otherwise stated.

Safety endpoints include AEs, clinical laboratory assessments, vital signs, physical examination, ECG parameters, and ECOG PS as described in Section 8.2.

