## Adverse Events

All AEs will be coded according to the MedDRA. Severity of AEs will be graded using the NCI-CTCAE v5.0 toxicity grading scale.

The incidence of treatment-emergent adverse events (TEAEs), regardless of attribution, and TEAEs defined as possibly related to M7824 will be summarized by MedDRA preferred term and system organ class (SOC) and described in terms of intensity and relationship to M7824. TEAEs are those events with onset dates occurring during the on-treatment period or if the worsening of an event is during the on-treatment period. Any AEs with an onset or worsening date after the on-treatment period will be reported separately.

The incidence of SAEs and AESIs will be summarized by preferred term and SOC.

Descriptive statistics will be examined for indications of dose-related ADRs.

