## Changes to the Planned Analyses in the Clinical Study Protocol

The statistical methods as described in the protocol were adopted. There are no changes to the planned analyses.

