- If both day and month are missing, the month and day will be imputed as December 31st
- If the date is completely missing, no imputation will be performed.

Note: In case the imputation results in a date later than the date of participant's death, then the date of death will be used to impute the incomplete stop date.

- **Missing data handling rules for subsequent anticancer therapy**

Incomplete dates for start date of subsequent anticancer therapy (drug therapy, radiotherapy, surgery) will be imputed as follows and will be used for determining censoring dates for efficacy analyses and in the derivation of the end of on-treatment period:

- If only day is missing, it will be imputed as the last day of the month unless the end date of subsequent anticancer therapy is before that date. In that case, the incomplete anticancer therapy start date will be imputed as the end date of the anticancer therapy.
- Otherwise it will not be imputed.

Incomplete subsequent anticancer therapy stop dates will not be imputed.

- **Missing data handling rules for death date**

For the purpose of survival analyses, partially missing death dates will be imputed as follows:

- If only the day is missing, the death date will be imputed to the maximum of the (non-imputed) day after the date of last known alive date and the 15th day of the month
- Otherwise it will not be imputed

- **Handling rules for tumor assessments**

- If there are multiple scan dates associated with an evaluation, the earliest of the scan dates associated with the evaluation will be used as the date of assessment

Partial dates, which are not to be imputed according to the IAP, will be presented in the format like " \_\_\_\_ YYYY". If values are imputed according to the IAP, imputed values will be presented in participant data listings and imputed information will be flagged.

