## 12.1 Previous and concomitant medications

**Previous medications** are medications, other than study medications, which started before first study intervention. In case the date values will not allow to unequivocally allocate a medication to previous medication, the medication will be considered as previous medication.

**Concomitant medications** are medications, other than study medications, which are taken by participants any time on-treatment (on or after the first day of study intervention for each participant) or within 30 days after last dose of study drug OR the earliest date of subsequent anticancer drug therapies minus 1 day, whichever occurs first. In case the date values will not allow to unequivocally allocate a medication to concomitant medication, the medication will be considered as concomitant medication. All medications starting the same day as study drug will be considered as concomitant. Medications starting the 30th days after the last dose of study treatment will also be considered as concomitant.

Specific rules will be used to define if a medication/procedure is considered as a previous, concomitant or both previous and concomitant medication/procedure as detailed in [Appendix 2](#).

Concomitant and previous medications are reported on the “Concomitant Medications Details” eCRF page.

Summaries of previous and concomitant medications will present the number and percentage of participants by drug class and preferred term according to the WHO-Drug B3 dictionary. Drug class will be derived as ATC classification Level 2, and the preferred term will be taken as the preferred drug name. If multiple ATCs are assigned to a drug, all ATCs for that drug will be reported.

A participant will be counted only once within a given drug class and within a given drug name, even if he/she received the same medication at different times.

Previous and concomitant medications will be presented in listing and include: participant identifier, age, sex, race, preferred term, medication name as provided by the Investigator, start date, end date, dose, dose units, frequency, route, reason for the medication.

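### SAP 9 also ends the default on-treatment period at post-discontinuation anticancer surgery or radiotherapy; Protocol 9.4.2 ends it early only at drug therapy, and SAP 7 declares no change

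*SAP*

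**What the plan says.** Protocol 9.4.2 runs the on-treatment period from first dose to last dose plus 30 days, "or the earliest date of subsequent anticancer drug therapy minus 1 day, whichever occurs first". Surgery and radiotherapy are not mentioned. Events that start or worsen in this period are TEAEs. For the rest the protocol says: "Any AEs with an onset or worsening date after the on-treatment period will be reported separately".

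SAP 9 (Definition of on-treatment period) keeps the 30 days but broadens what can end the period early. It counts as subsequent therapy "Any systemic anticancer therapy, any anticancer surgery and any anticancer radiotherapy as documented in the" case report form page for anticancer treatment after discontinuation. It then restates the rule so that the period ends at "subsequent anticancer drug (anticancer therapy, anticancer surgery and anticancer radiotherapy) therapy minus 1 day". The SAP 9 rule for incomplete dates names drug therapy, radiotherapy and surgery start dates, and says that they are "used for determining censoring dates for efficacy analyses and in the derivation of the end of on-treatment period".

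Other SAP text points the other way:
- SAP 7 says of the protocol's methods: "There are no changes to the planned analyses".
- The SAP modification history records only the addition of the re-initiation period to this definition.
- SAP 12.1 sets the concomitant-medication window at "within 30 days after last dose of study drug OR the earliest date of subsequent anticancer drug therapies minus 1 day", which is the protocol's drug-only cut.
- SAP 14.4 exempts palliative bone radiotherapy when it defines new anticancer therapy for PFS censoring. SAP 9 has no such exemption.

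On re-initiated treatment, SAP 9 says: "The on-treatment period will include the initial treatment period as well as the reinitiation of treatment period, as applicable". SAP 9 (Data collected after re-initiated treatment) and SAP 15.1 likewise put re-initiation data and adverse events into the summaries.

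**The concern.** Occurrence of TEAEs is a stated secondary endpoint, and the analyses in SAP 15.1 use TEAEs unless otherwise specified. The end of the on-treatment period therefore decides which events are tabulated. The SAP changes that boundary in one direction only: for the default 30-day window, its end date can equal the protocol's or fall before it. An event that begins after local therapy but within 30 days of the last dose is a TEAE under the protocol. Under the SAP it leaves the TEAE tables and appears only in a listing. A reader who relies on SAP 7 would not know this. The same period also bounds the SAP's worst-grade laboratory, liver-function and ECOG shift summaries.

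There is a second problem inside the SAP. Its rule takes whichever end date comes first and applies whether or not treatment is re-initiated. Local therapy between discontinuation and re-initiation would close the period before the re-initiated infusions, although three SAP statements say those data are included.

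**Working it through.** **Inputs.** The default extension is 30 days after the last dose (Protocol 9.4.2, SAP 9). The early end is the day before the triggering therapy (both documents). The trigger is drug therapy only in the protocol, and drug therapy, surgery or radiotherapy in the SAP. The plan gives no figure of its own to reproduce.

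**Without re-initiation.** Count days from the last dose as day 0. Let local therapy start on day k, with no earlier anticancer drug.
- Protocol end = 30.
- SAP end = min(30, k − 1).
- Days lost = 30 − (k − 1) = 31 − k for k from 1 to 30, and 0 for k of 31 or more.

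| k | Protocol end | SAP end | Days lost | Share of the 30 days |
|---|---|---|---|---|
| 1 | 30 | 0 | 30 | 100% |
| 7 | 30 | 6 | 24 | 80% |
| 14 | 30 | 13 | 17 | 57% |
| 21 | 30 | 20 | 10 | 33% |
| 30 | 30 | 29 | 1 | 3% |
| 31 or more | 30 | 30 | 0 | 0% |

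**With re-initiation.** Count from the last dose of the initial course, and let the last re-initiated dose be on day L.
- Protocol end = L + 30, if no anticancer drug was given.
- SAP end by its formula = k − 1, where k is the day of local therapy before re-initiation.
- Days lost = L + 31 − k.

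As a hypothetical case, take radiotherapy on day 60 and six infusions two weeks apart on days 74, 88, 102, 116, 130 and 144. The protocol window ends on day 144 + 30 = 174 and the SAP formula on day 60 − 1 = 59. The difference is 174 − 59 = 115 days, and all six infusions fall outside. This shows how the formula behaves; it is not an expected case.

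**Which events move.** Protocol 7.2 asks for the Safety Follow-up visit to be brought forward before any new therapy. After that visit, Protocol 8.3.1 collects serious events and non-serious treatment-related events. Where the visit has been brought forward, the events moved out of the tables are mainly of those kinds.

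**How many participants.** The documents give no rate of surgery or radiotherapy soon after the last dose, so the count cannot be computed.

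**The case against.** The best defence is that the wider cut is reasonable. Protocol 7.2 moves the follow-up visit ahead of any new therapy, not only drug therapy, and adverse event collection narrows afterwards. Keeping that interval in the TEAE tables mixes periods with different ascertainment. Protocol 9.4.2 also allows for exceptions stated elsewhere and leaves further safety detail to the analysis plan. The first part stands: the wider cut could be chosen deliberately. The second does not remove the conflict, because SAP 9 rewrites the default rule itself while SAP 7 says nothing has changed.

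The SAP's inclusion sentences on re-initiation also show its intent, and the protocol formula would close early in the same way if a drug were given before re-initiation. The case is rare as well: the category listed in Protocol 7.1.2 is participants in complete response at discontinuation who later progress. All of that is fair, but a programmer who follows the written formula would still exclude data that the SAP says to include.

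A reader might infer more than the documents support:
- *That any surgery or radiotherapy ends the period.* SAP 9 ties the trigger to treatment recorded after discontinuation, so local treatment given while study treatment continues would not normally count. The page reference is itself unclear, since SAP 12.5 puts radiotherapy and surgery on separate pages, but the incomplete-date rule confirms that both are meant to count.
- *That the SAP window is never longer than the protocol's.* This holds only for the default window. SAP 9 gives immune-related events 90 days, a separate rule outside this point.
- *That events disappear from the report.* They stay in the listings, and the protocol also reports later events separately. What differs is where the boundary falls.

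**Conclusion.** The point holds for the default 30-day window. SAP 9 applies a wider early-end trigger than Protocol 9.4.2, SAP 7 does not declare it, and SAP 12.1 and SAP 14.4 are not consistent with it. The loss is 31 − k days per affected participant. It requires local therapy recorded after discontinuation and within 30 days of the last dose, with no earlier anticancer drug; a TEAE count changes only if an event starts or worsens in the lost days. The number affected is unknown and probably small. The re-initiation conflict is real on the wording but rare, and there the loss is not capped at 30 days. The primary test of objective response rate and the count of deaths within 30 days of last dose do not depend on this definition. The point should be corrected, but it does not threaten the trial's main conclusion.

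**What to change.** In SAP 9, end the default on-treatment period early only at subsequent anticancer drug therapy, as in Protocol 9.4.2 and SAP 12.1, and bring the incomplete-date rule into line. If the wider cut is intended, declare it in SAP 7 with the reason, and also tabulate TEAEs under the protocol definition.

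In either case, state that for participants who re-initiate, therapy given before re-initiation does not close the period ahead of the re-initiated doses. SAP 9 then agrees with its own inclusion sentence and with SAP 15.1.

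The cost is SAP wording and one derived end date, with no new data collection. Aligning with the protocol can only leave default-window TEAE counts unchanged or raise them. The alternative costs a short entry in SAP 7 and one extra set of TEAE tables.

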### Unscheduled assessments:

As per database definition, the safety unscheduled assessments are always linked to a scheduled timepoint (each unscheduled assessment is linked to the previous scheduled timepoint). Safety data retrieved from an unscheduled timepoint (vital signs, electrocardiogram [ECG] and laboratory data) will be analyzed according to the following scenario:

- For shift table, they will be taken into account in the definition of the worst assessment during study
- For description at each timepoint post-baseline, the first available result (in chronological order) per timepoint will be taken into account in the analysis in case of multiple values
- For description at baseline, the last available result before first study intervention will be taken into account in the analysis in case of multiple values

For immunogenicity analysis, unscheduled visits will also be taken into account in the analysis following the same rules as detailed above.

For PK analysis, unscheduled samples will not be linked to a scheduled timepoint and will be excluded from summaries.

#### **Definition of duration:**

Duration will be calculated by the difference between start and stop date + 1 if not otherwise specified. For example, duration of response (days) = date of PD/death/censoring – date of response + 1.

The time since an event (e.g. time since initial cancer diagnosis) will be calculated as reference date minus date of event. In general, the reference date will be the date of first study intervention.

The time to an event will be calculated by the difference between the time of event and the reference date + 1 if not otherwise specified. For example, survival time (days) = date of death - date of first study intervention + 1.

#### **Common calculations:**

For quantitative measurements, change from baseline will be calculated as:

- Test Value at timepoint X – Baseline Value

#### **Conversion factors:**

The following conversion factors will be used to convert days into months or years:

- 1 month = 30.4375 days
- 1 year = 365.25 days

#### **Handling of missing data:**

Unless otherwise specified in this IAP, missing data will not be replaced.

Missing statistics, e.g. when they cannot be calculated, should be presented as “nd” for “not determined. For example, if n=1, the measure of variability [e.g. standard deviation (StD)] cannot be computed and should be presented as “nd”.

#### **Handling of incomplete dates:**

- **Missing data handling rules for age calculation**

Incomplete dates (date of informed consent, date of birth) for the calculation of age will be imputed as follows:

- In case of missing day for at least one date, but month and year available for both dates: the day of informed consent and the day of birth will be set to 1.

- In case of missing month for at least one date, but year available for both dates, the day and the month of informed consent and the day and month of birth will be set to 1.
- In all other cases, the incomplete dates will not be imputed.

- **Missing data handling rules for disease history**

Incomplete dates for disease history (date of initial diagnosis date, date of documented, locally advanced, inoperable or metastatic disease diagnosis, date of response or progression in prior treatment) will be imputed as follows:

- If the day is missing, it will be imputed to the 1st day of the month.
- If both day and month are missing, the month and day will be imputed as January 1st
- If the date is completely missing, no imputation will be performed.

- **Missing data handling rules for adverse events**

Incomplete AE-related dates will be imputed as follows:

- In case the onset date is missing completely or missing partially but the onset month and year, or the onset year are equal to the start of study treatment, then the onset date will be imputed by the minimum of start of study treatment and AE resolution date (if not missing).
- In all other cases, the missing onset day or missing onset month will be imputed by 1.
- Incomplete stop dates will be imputed by the last day of the month (if day is missing only), if not resulting in a date later than the date of participant's death. In the latter case, the date of death will be used to impute the incomplete stop date.
- In all other cases, the incomplete stop date will not be imputed.

- **Missing data handling rules for previous and concomitant medications**

Incomplete dates for previous and concomitant medications will be imputed as follows:

For start date of medication

- If the day is missing, it will be imputed to the 1st day of the month.
- If both day and month are missing, the month and day will be imputed as January 1st.
- If the date is completely missing, no imputation will be performed.

For end date medication:

- If the day is missing, it will be imputed to the last day of the month.
- If both day and month are missing, the month and day will be imputed as December 31st
- If the date is completely missing, no imputation will be performed.

Note: In case the imputation results in a date later than the date of participant's death, then the date of death will be used to impute the incomplete stop date.

- **Missing data handling rules for subsequent anticancer therapy**

Incomplete dates for start date of subsequent anticancer therapy (drug therapy, radiotherapy, surgery) will be imputed as follows and will be used for determining censoring dates for efficacy analyses and in the derivation of the end of on-treatment period:

- If only day is missing, it will be imputed as the last day of the month unless the end date of subsequent anticancer therapy is before that date. In that case, the incomplete anticancer therapy start date will be imputed as the end date of the anticancer therapy.
- Otherwise it will not be imputed.

Incomplete subsequent anticancer therapy stop dates will not be imputed.

- **Missing data handling rules for death date**

For the purpose of survival analyses, partially missing death dates will be imputed as follows:

- If only the day is missing, the death date will be imputed to the maximum of the (non-imputed) day after the date of last known alive date and the 15th day of the month
- Otherwise it will not be imputed

- **Handling rules for tumor assessments**

- If there are multiple scan dates associated with an evaluation, the earliest of the scan dates associated with the evaluation will be used as the date of assessment

Partial dates, which are not to be imputed according to the IAP, will be presented in the format like " \_\_\_\_ YYYY". If values are imputed according to the IAP, imputed values will be presented in participant data listings and imputed information will be flagged.

### **Treatment day**

Day 1 is the day of start of study intervention, the day before is Day -1 (no Day 0 is defined). Study day/Study intervention day is defined relative to Day 1.

### **Preferred term for analysis of WHO-DD coded data**

For data coded according to WHO Drug B3 (e.g., concomitant medications), summaries will be done on the preferred term level where the preferred term is corresponding to codes ending in 01001. With this approach, variations of salt forms of active ingredients will be analyzed under the same term, e.g. diphenhydramine and diphenhydramine hydrochloride will be analyzed as the same preferred term diphenhydramine.

**Re-screened participants:**

Re-screened participants will be only counted once in the screening analysis set, considering the latest screening (screening with latest informed consent).

**Data collected after re-initiated treatment:**

Data collected after re-initiation of treatment will be included in the summary statistics. A data listing will include AE data for all reinitiated participants.

**Categorization of participants for COVID-19 impact assessment**

For the assessment of COVID-19 impact on this study, participants will be categorized as being affected by COVID-19 (either due to infection or due to circumstances of social distancing affecting the capabilities of sites/hospitals etc.) based on the COVID-19 study period defined as:

- The start of COVID-19 study period will be defined by country as the minimum of the date of the first death from COVID-19 occurred in each country according to the published data by European Centre for Disease Prevention and Control on 26th June 2020 and 11 March 2020 (WHO-start of world-wide pandemic).
- Post-pandemic could be defined as date (1) vaccination is released, (2) WHO declares COVID-19 pandemic over, (3) region-specific calls are made to end social distancing measures with no relevant rise in cases thereafter. As study treatment for the last participant started on 3rd January 2020, no participant will be grouped into the post COVID-19 study period for this study and no post-pandemic date will be defined.

Participants will be categorized into subgroups according to the methods shown in [Table 4](#) depending on the purpose of analysis.

**Table 4** Types of categorization for COVID-19 assessment

Type of categorization	Subgroup	Definition
Categorization for assessment on efficacy	Pre	Participant started treatment prior to and had progressive disease or died or withdrew from tumor assessments prior to COVID-19 study period
	During	Participant started treatment prior to or during COVID-19 study period and had any tumor assessments during the COVID-19 study period
	Post*	Participant started treatment post the COVID-19 study period
Categorization for assessment on safety without time window	Pre	Participant started treatment prior to COVID-19 study period
	During*	Participant started treatment during the COVID-19 study period
	Post*	Participant started treatment post the COVID-19 study period
Categorization for assessment on safety with time window	Pre	Participant started treatment 3 months prior to COVID-19 study period
	During	Participant started treatment on or after the date 3 months prior to COVID-19 study period
	Post*	Participant started treatment post the COVID-19 study period

\* No participants will be categorized into the 'post COVID-19 study period' or the 'during COVID-19 study period for safety without time window' for this study.

